# 7. Study Overview

#### 7A. Overall objective

#### 7A1. Overall objective for Phase I/IIa anakinra study

The goal of this study is to determine the safety, pharmacokinetics and activity of anakinra in acute KD patients with coronary artery Z score  $\geq$  2.5. The goal will be to find a treatment that could prevent or attenuate coronary artery damage in acute KD.

#### 7A2. Overall objective for Combination therapy pilot study

The goal of this study is to determine the safety and activity of these two drugs in combination in acute KD patients with coronary artery Z score  $\geq$  2.5. The goal will be to find a treatment regimen that could prevent or attenuate coronary artery damage in acute KD.

#### 7B. Hypothesis

#### 7B1. Hypothesis for Phase I/IIa anakinra study

We postulate that anakinra will be safe in infants and children with acute KD.

#### 7B2. Hypothesis for Combination therapy pilot study

We postulate that anakinra and atorvastatin in combination will be safe in children with acute KD. We also postulate that this combination therapy will reduce inflammation in children with acute KD more than using anakinra or atorvastatin alone.

## 7C. Study Type

#### 7C1. Hypothesis for Phase I/IIa anakinra study

This is a Phase I/IIa, dose escalation study.

#### 7C2. Hypothesis for Combination therapy pilot study

This is a pilot study.

### 7D. Study Population

#### 7D1. Study population for Phase I/IIa anakinra study

Infants and children with acute KD who have a Z-score  $\geq 2.5$  of the left anterior descending (LAD) or right coronary arteries (RCA).

#### 7D2. Study population for Combination therapy pilot study

Children with acute KD who have a Z-score  $\geq$  2.5 of the LAD or RCA.

### 7E. Study Duration

#### 7E1. Study duration for Phase I/IIa anakinra study

The entire study will last 5 years. Each subject will be in the study for 6 weeks.

#### 7E2. Study duration for Combination therapy pilot study

The entire study will last 5 years. Each subject will be in the study for 6 weeks.

#### 7F. Primary Outcome

#### 7F1. Primary Outcome for Phase I/IIa anakinra study

Safety of anakinra in the study population

#### 7F2. Primary Outcome for Combination therapy pilot study

Safety of anakinra and atorvastatin in combination

## 7G. Secondary Outcomes

#### 7G1. Secondary Outcomes for Phase I/IIa anakinra study

- 1. Pharmacokinetics of anakinra
- 2. Immune-monitoring pre-and post-therapy
  - a. Enumeration of myeloid dendritic cell populations
  - b. Enumeration of activated CD4+ and CD8+ DR+ T cells, enumeration regulatory T cells
- 3. Measures of inflammation pre-and post-therapy
  - a. Transcript abundance changes over time by RNAseq
  - b. Levels of high sensitivity (hs) C-reactive P (CRP), alpha-1 antitrypsin, TNFaR1 and R2, IFNg, IL-1 RAP, IL-1R1 and R2, MMP9, caspase-1, IL-6R, IL-18RAP, IL-12, IL-2, TGFb and IL-10
- 4. Echocardiographic assessment of coronary artery internal diameters expressed as Z scores pre-and post-therapy

#### 7G2. Secondary Outcomes for Combination therapy pilot study

[figure not shown]
- 1. Measures of inflammation
  - a. Plasma levels of IL-1R accessory protein, soluble IL-1R1, IL-17, IL-6, sIL-6R, TNF $\alpha$ R1, IFN $\gamma$ , IL-10, and MMP9

- b. Transcript abundance changes over time by RNAseq of the above analytes
- 2. Endothelial cell function studies to evaluate for suppression of the innate immune response by anakinra and restoration of EC function by atorvastatin.
- 3. Echocardiographic assessment of coronary artery internal diameters expressed as Z scores

# 8. Background & Significance

#### 8A. Significance

Kawasaki Disease (KD), the most common cause of acquired heart disease in children in Western developed countries and Asia, is a systemic vasculitis of unknown etiology. In the United States, there are at least 5-6,000 new cases each year (Kaneko 2011). However, without a specific diagnostic test, the true burden of disease is unknown. At Rady Children's Hospital San Diego, we cared for over 85 new KD patients in 2013 and follow over 1,200 families in our outpatient KD Clinic (350 outpatient visits/year), of whom 9% developed aneurysms and 25% developed dilated coronary arteries. In Japan, the country of highest incidence (>215/100,000 children < 5 yrs.), there are more than 12,000 new cases each year and rates continue to rise (Nakamura 2010). KD causes both a myocarditis and a vasculitis that damages the coronary arteries and other mediumsized muscular arteries (Yutani 1980, Yonesaka 1989). The major sequelae of aneurysms include thrombosis, late coronary artery stenosis, myocardial ischemia, myocardial infarction, and death (Kato

[figure not shown]

1996, Gordon 2009). Clearly, aneurysm prevention is a primary goal of treatment during the acute phase of the disease, which leads us to focus on treatment of patients with early signs of coronary artery abnormalities (CAAs) in this pilot study.

Intravenous immunoglobulin (IVIG) in combination with aspirin is the only approved therapy for KD. The major acute risk of aneurysm formation is thrombosis, which can be prevented with systemic anti-coagulation with warfarin or enoxaparin in addition to antiplatelet therapy with aspirin or clopidogrel in patients with large aneurysms (>6 mm). However, there is no recommended therapy to halt the progression of arterial wall destruction and prevent aneurysm formation beyond the initial dose of IVIG.

#### 8A1. Role of IL-1 pathway in KD and blockade by anakinra

In KD, the IL-1 pathway is upregulated, as demonstrated by increased transcript abundance by microarray and by increased levels of pathway proteins in the plasma (Maury 1988, Leung 1989, Popper 2007, Hoang 2014). (**Figure 2 and Table 1**)

controls) and shared among KD, viral and bacterial infection groups. Pathways are ordered by descending log (p-value). Individual probe P values are uncorrected. Yellow highlighting identifies transcripts that were significant in more than one pathway. Red box identifies transcripts in the IL-1 pathway.

Furthermore, in the *Lactobacillus casei* cell wall extract mouse model that develops a KD-like coronary arteritis, the IL-1 receptor antagonist, anakinra, prevented the development of coronary lesions, as did knocking out the IL-1 receptor (Lee 2012). Anakinra has been used to treat a severe KD patient who was non-responsive to IVIG treatment (Cohen 2012).Treatment with anakinra was safe and coincided with a decrease in systemic and coronary artery inflammation. The proposed study will determine if anakinra is safe to use in young children with KD and has demonstrable anti-inflammatory activity at a well-tolerated dose. Assessments of drug activity will allow us to determine appropriate end-points for a future Phase III study to address the efficacy of anakinra in attenuating vascular wall damage and preventing aneurysms in KD patients.

### 8B. Use and safety of anakinra in infants and children

Anakinra is currently used in several inflammatory diseases in infants and children, including systemic juvenile idiopathic arthritis and the autoinflammatory syndromes known as cryopyrinassociated periodic syndromes (CAPS)(Hoffman 2009, Ringold 2013). In a recent study of 26 patients with the autoinflammatory syndrome neonatal-onset multisystem inflammatory disease (NOMID), treatment with anakinra for 36 months had a low adverse event rate, with upper respiratory infection as the most commonly reported complication (Sibley 2012). A similar study using anakinra in another CAPS, Muckle Wells syndrome, did not demonstrate any SAEs in the 12 patients treated with anakinra, of whom 5 were children (Kuemmerle-Deschner 2011). Two case reports have been published reporting the use of anakinra in children with refractory, acute KD. A 2 year old with giant aneurysms who failed therapy with IVIG and steroids and developed giant aneurysms was treated with a 6 week course of anakinra at 1 mg/kg (Cohen 2012). He suffered no adverse effects and at 6 months coronary angiography demonstrated resolution of the aneurysms, which was unexpected in such a severe case of KD. An 11 week old with KD and giant aneurysms was refractory to three doses of IVIG, steroids and a dose of infliximab (Shafferman 2014). She was treated with anakinra initially at 6 mg/kg/day and then increased to 9 mg/kg/day. She too did not suffer any adverse effects and at an 8 month follow up visit her coronary artery status had also significantly improved.

Given that this medication is administered once daily as a subcutaneous injection, the most common adverse reaction is irritation at the injection site. Table 2 is a summary of published and unpublished data on the use of anakinra in children <2 years old:

Ages Treated (in months)	Max Dose (mg/kg)	Diagnosis	Reference
17	1.6	CINCA	(Matsubara 2006)
3 and 4	6 & 10	NOMID	(Neven 2010)
2,4,13 and 22	1-4	DIRA	(Aksentijevich 2009)
1	1	DIRA	(Stenerson 2011)
8	11	sJIA	(Record 2011)
10 and 18	2-4	sJIA	(Nigrovic 2011)
5	3	DIRA	(Minkis 2012)
10, 13, 16, 20	2-4	NOMID	(Sibley 2012)
18	8	MVK	(Ruiz Gomez 2012)
24	9	KD	(Cohen 2012)
6	2-4	Def IL-36Ra	(Rossi-Semerano 2013)
8	2-10	sJIA	(Urien 2013)
3 and 14	2-3	MVK	(Levy 2013)
6	2	NOMID	(Montealegre 2014)
2	9	KD & MAS	(Shafferman 2014)
12 and 15	6 & 8	CAPS	(Hoffman 2014)
18	15	sJIA & MAS	(Cartwright 2014)
11	8	CAPS	(Jerath 2014)
13**	4	sJIA	(Momborquette 2014)
15 and 18	3.5 & 4	CINCA & sJIA	(Guedes 2014)
10, 15, 17, and 22	1 to 9	sJIA	(Punaro 2014)
6, 9 and 15	1-3	CAPS	(Ombrello 2014)
20	5	Hyper IgD Syndrome	(Ombrello 2014)

Table 2 Llas of analying in shildran < 2 years . . CINCA = chronic infantile, neurological, cutaneous and arthritis; NOMID = neonatal onset multi-system inflammatory syndrome (CINCA and NOMID are the same syndrome); DIRA = deficiency of the IL-1 receptor antagonist; sJIA = systemic juvenile idiopathic arthritis; MVK = mevalonate kinase deficiency; KD = Kawasaki disease; MAS = macrophage activation syndrome; CAPS = cryopyrin associated periodic syndrome

No adverse effects noted besides mild local reaction unless otherwise noted; \*\*coxsackie virus while also on methotrexate and steroids;

Thus, at least 39 children < 2 years of age, and as young as 2 months of age, have been treated with anakinra with doses ranging from 1 to 15 mg/kg.

#### 8C. Safety of atorvastatin in children

The safety of atorvastatin in children as young as 2 years of age with acute KD was assessed in a Phase I/IIa dose escalation study (IND 113304 issued to [name], co-investigator of this study). On May 19, 2016, the DSMB for this Phase I/IIa study evaluated the data from the Phase I dose-escalation study of atorvastatin for 6 weeks in children at least 2 years with acute KD and coronary artery damage. The DSMB determined that a 6 week course of atorvastatin was safe and well-tolerated in children  $\geq$  2 years with acute KD. In addition, based on the review of the safety of the Phase I study, the DSMB determined 0.75 mg/kg/day of atorvastatin to be the maximum tolerated dose. An additional 10 subjects were enrolled at 0.75 mg/kg/day as part of the dose expansion cohort study and further demonstrated the safety and tolerability of this dose in acute KD. The level of the cholesterol brain metabolite, 24-OH cholesterol, was measured in both statin-treated KD patients and in those treated with standard therapy for KD. No significant difference was found between the groups in the levels of 24-OH cholesterol, further demonstrating the safety of atorvastatin in acute KD as it does not reduce the levels of 24-OH cholesterol, which are important for normal brain development.

On August 1, 2017, this original Phase I/IIa dose-escalation and expansion cohort study was completed. On August 4, 2017, an annual report of the atorvastatin IND was sent to the FDA demonstrating that there had been no unexpected, adverse events in this study and that atorvastatin was safe and well-tolerated. An abstract reporting the results of the Phase I study has been accepted for poster presentation at the American Heart Association in November 2017.

#### 8D. Importance of the problem

Once aneurysms have formed, there is no way to turn back the biologic clock and undo them. The transmural inflammation destroys the normal architecture and even in children who remodel the aneurysm to form a more normal lumen, the vessel is never functionally normal again. The remodeled segment cannot dilate normally during increased myocardial oxygen demand and thus serves as a functional stenosis. It has been estimated that there are currently over 24,000 young adults in the United States with a history of KD, including over 8,000 with a history of coronary artery abnormalities. Without a new therapeutic approach this number is expected to grow by 1,400 individuals each year (Gordon 2009). A recent study found that over 5% of all young adults (<40 years) evaluated by cardiac catheterization for suspected myocardial ischemia have aneurysms compatible with antecedent KD (Daniels 2012).

#### 8E. Ongoing KD European clinical trial of anakinra

Sobi Pharmaceuticals, the manufacturer of Kineret® (anakinra), is currently supporting a clinical trial in Europe, treating IVIG-resistant KD patients ( $\geq$  8 months of age) with a 14-day course of anakinra. In this trial, there will be within-subject dose escalation starting at 2mg/kg and increasing every 24h through 4 mg/kg and 6 mg/kg based on persistence of fever.

#### 8F. Potential to effect change in clinical practice

# **8F1. Potential of Phase I/IIa anakinra trial to effect change in clinical practice** The current clinical practice is to give every patient the same standard therapy (IVIG 2g/kg with aspirin 30-50/kg) and to monitor for CAA. In the unfortunate child who carries the genetic risk for CAA, no intervention to modify vessel wall inflammation is currently recommended (Newburger 2004).

In a recent article entitled "Mining for therapeutic gold", Director of the NIH, [name], stated that "repurposing" therapeutics should be a strategy "to translate research into clinically useful products" (Collins 2011). Our goal is to translate our findings on the role of the IL-1 pathway in acute KD and "repurpose" anakinra to test the hypothesis that the anti-inflammatory properties of this drug will prevent or attenuate coronary artery aneurysms in infants and children with KD.

#### **8F2.** Potential of Combination therapy pilot study to effect change in clinical practice Our goal is to translate our findings on the role of the IL-1 pathway and EndoMT in acute KD and

"repurpose" anakinra and atorvastatin in combination to test the hypothesis that the anti-inflammatory properties of these drugs in combination will prevent or attenuate coronary artery aneurysms in children with KD.

### 8G. Paradigm shift if Specific Aims are achieved

By performing this study, we will bring to the forefront the need for new therapies for the subset of KD patients who are genetically predisposed to develop coronary artery damage. The paradigm shift will be to intensify initial therapy for KD patients, thus acknowledging the urgency of early intervention to prevent the permanent disability associated with aneurysm formation. Furthermore, given the unique immunological expertise within our group, demonstration of the immunomodulatory effects in a cardiovascular disease could pose a novel treatment for other cardiovascular diseases.

# 9. Hypotheses and Specific Aims

## 9A. Specific Aims for anakinra Phase I/IIa study

# Specific Aim 1 will test the hypothesis that a 2-6-week course of anakinra will be safe and well-tolerated in infants and children with acute KD who have a Z-score $\geq$ 2.5 of the LAD or RCA.

The safety of anakinra will be assessed by monitoring for leukopenia, clinical and laboratory signs of infection, and injection site reactions.

# Specific Aim 2 will describe the pharmacokinetics of anakinra and test the hypothesis that anakinra will decrease systemic and coronary artery inflammation associated with acute KD.

Blood will be tested pre-drug administration, 48 hours after initiation of therapy and at 2 weeks and 6 weeks for markers of inflammation and enumeration of dendritic cells and T cells. Echocardiographic assessment of CAA at these time points will be compared to historical controls matched for age, sex, illness day at diagnosis, and coronary artery status on initial echo.

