#### 11G. Echocardiography Core Lab for Phase I/IIa anakinra study and Combination therapy pilot study

An echocardiogram will be performed at the following time points:

- During initial hospitalization (as soon after admission as possible)
- 48 hours after enrollment in this study
- Study week 2 (Study day 14 ± 7 days)
- Study week 6 (Study day 42 ± 7 days)

2-D transthoracic echocardiograms (2-D Echo) will be performed on all KD subjects according to a strict pre-determined protocol at standard of care time points. All echocardiographic images will be analyzed by [name], Director of Non-Invasive Cardiovascular Imaging at Rady Children's Hospital San Diego. She will be blinded to patient data and clinical status. [name] will also assure adherence to the echo protocols across all echocardiogram technicians. 2-D Echo will be performed at KD diagnosis (within 24h of IVIG infusion) and again at two and six weeks following enrollment with sedation when clinically indicated. The internal lumen diameters of the left main (LMCA), proximal and distal LAD, circumflex, posterior descending, and proximal and distal RCA will each be measured. Dimensions of the LMCA, proximal LAD, and proximal RCA will be adjusted for body surface area and expressed in standard deviation units (Z-scores) (Manlhiot 2009). A variable "Z worst any vessel" will be created to capture the maximal Z score of the RCA or LAD at any time point, as well as the Z-score of the LMCA if an aneurysm is present there with a Z-score larger than that of the RCA or LAD. Coronary artery aneurysm will be defined as a Z-score of 2.5 or larger of the RCA or LAD(Nishiike 2006).

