# 11H. Data Management for Phase I/IIa anakinra study and Combination therapy pilot study

Subjects will be assigned a unique study number. Demographic and clinical information including all numerical echo data parameters will be entered into an established, password-protected, database in use by our research group since 2001 (http://www-pediatrics.ucsd.edu/kawasaki) that currently contains data on over 1,200 KD subjects. The web portal uses the secure web application Research Electronic Data Capture (REDCap) (Harris 2009).

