# 18. Measures of Activity

#### 18A. Measures of inflammation for Phase I/IIa anakinra study

Transcript abundance will be measured in whole blood by microarray. Levels of hsCRP,  $\alpha$ -1antitrypsin and fibrinogen, and the WBC and ESR will be measured in the hospital clinical laboratory. Levels of TNFaR1 and R2, IFNg, IL-1 RAP, IL-1R1 and R2, MMP9, caspase-1, IL-6R, IL-18RAP, IL-12, sIL-2R, TGFb and IL-10 will be measured by ELISA. Results of transcript abundance and measures of inflammation will be compared to database controls from the KD Research Center (>600 KD patients with available RNA and plasma samples in our biorepository) matched (1 case: 2 controls) by age (± 2 yrs. with lower limit of 2 yrs.), sex, and coronary artery Z-score.

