#### 19B. Statistical analysis of inflammatory studies

**19B1. Statistical analysis of inflammation studies for Phase I/IIa anakinra study** The objective of this matched case-control study is to determine the activity profile of anakinra in the treatment of KD subjects with CAA. Measures of inflammation will be compared to that of matched controls via paired statistical tests (e.g. McNemar's test for categorical outcomes or the paired t-test for continuous outcomes). Non-parametric alternatives will be considered only if distributional assumptions are violated.

**Control Group:** Controls will be chosen from the >600 subjects with data in our web-based data repository in REDCap. Controls will be matched to study patients based on age, sex, Illness Day at diagnosis, and baseline Z score.

**Analysis:** Each marker will be initially summarized descriptively and analyzed individually. Separate multivariable mixed effects regression modeling for clustered data (to account for the case-control paired nature of samples) will be used to characterize the markers of anakinra-treated subjects versus matched controls to adjust for any known confounders and additional time points (baseline, 48 hours, 2 weeks, and 6 weeks). In addition, any covariate at the individual level that is simultaneously unbalanced and associated with the outcome will be included in the model. Covariates of interest include demographic variables (e.g., ethnicity, Illness Day at diagnosis, response to IVIG therapy). Permutation tests may be implemented to verify that valid p-values will be obtained even if model assumptions are not correct. Note that the mixed model seamlessly accommodates different times of measurement (e.g. 2-week and 6-week time points) as well as missed measurements and data from subjects who are lost to follow-up. A corresponding Generalized Estimating Equations (GEE) model will be used as the sensitivity analysis method. An analogous secondary model including all subjects in this study will also be considered to examine the dose versus activity relationship. In this model, dosage will be included as a covariate to examine any dosage trend in activity.

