The above approach will be repeated for the other markers. That is, multi-level mixed effects regression models analogous to the above methodology will be applied for other markers: Levels of high sensitivity (hs) CRP, alpha-1 antitrypsin, TNFaR1 and R2, IFNg, IL-1 RAP, IL-1R1 and R2, MMP9, caspase-1, IL-6R, IL-18RAP, IL-12, IL-2, TGFb and IL-10.

Measures of transcript abundance will also be analyzed via microarray analysis. Data will be preprocessed first and then microarray analysis procedures will be used to measure abundance. The R software (version 3.0.2) and Bioconductor package in R will be used for the analysis. For coronary outcomes as assessed by echocardiography, we will compare the delta Z scores (baseline minus 2weeks and 6-weeks) between anakinra subjects and matched controls. A GEE model will be used as the sensitivity analysis method. Since this is a safety and early efficacy study, no adjustments for multiple comparisons will be made for biomarker analyses. P-values less than 0.05 will be considered statistically significant. All statistical analyses will be performed in R version 3.2.0 (www.rproject.org/). Similarly, analyses will be repeated on all subjects to characterize any dose-activity relationship, adjusting for dosage as a covariate in the model.

To determine the "best" or "set of best" markers that have the greatest improvement from baseline in anakinra-treated patients, ROC and AUROC analysis will be considered. In the event that there is

high multi-collinearity amongst the markers, we will adopt the "glmpath" approach, which is based on Least Angle Regression (LARS) methods to select the best biomarkers (Park 2007).

Missing data assumptions: The proposed mixed-effects regression model is consistent under the assumption that the outcome data are "missing at random" (MAR), that is, mixed models with a random effect assume only that the probability that an outcome is missing depends on observed outcomes. GEE models, which are proposed as a sensitivity analysis, assume that the outcome data are "missing completely at random", that is, that the probability that an outcome is missing does not depend on any previous, present or succeeding value of the outcome. This will enable us to assess the impact of the missing data mechanism on statistical inferences drawn from these models.

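### Nothing in the plan keeps follow-up outcomes out of view when historical controls are chosen, and the matching rule is loose and inconsistent enough to leave a choice, so outcome knowledge could shape the secondary delta-Z comparison.

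*Combined protocol and SAP*

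**What the plan says.** **Comparison.** Neither study has a randomised comparator. For anakinra, section 9A (Specific Aim 2) says that echo findings "will be compared to historical controls matched for age, sex, illness day at diagnosis, and coronary artery status on initial echo". Section 19B1 adds that "we will compare the delta Z scores (baseline minus 2weeks and 6-weeks) between anakinra subjects and matched controls", and 19B2 plans the same contrast for the combination study.

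**Source of controls.** Section 19B1 states: "Controls will be chosen from the >600 subjects with data in our web-based data repository in REDCap". Section 19B2 says the same. Section 11H says that background and clinical data, "including all numerical echo data parameters will be entered into an established, password-protected, database in use by our research group since 2001".

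**Matching rule.** Section 19B1: "Controls will be matched to study patients based on age, sex, Illness Day at diagnosis, and baseline Z score". Section 18A, for transcripts and inflammation markers, has controls "matched (1 case: 2 controls) by age (± 2 yrs. with lower limit of 2 yrs.), sex, and coronary artery Z-score". Section 15A assumes 18 controls for 18 cases. For the combination study, 15B assumes 10 for 10, while 18B lists control groups of 20, 10 and 10.

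**Masking.** Section 11G says of the echo reader: "She will be blinded to patient data and clinical status". No other masking is stated.

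**The concern.** A historical control has already finished follow-up. Section 11D treats echo at 2 and 6 weeks as standard of care in children with coronary abnormalities, and the delta-Z contrast cannot be computed unless those values exist for controls. Whoever picks controls from the repository may therefore be able to see how each candidate did. If several children fit a case and no rule decides between them, that knowledge can influence which one is taken, even without intent. Choosing less favourable courses would make the drug look active when it is not.

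None of the planned analyses would detect or remove this. Mixed models, GEE, covariate adjustment and permutation tests all take the chosen controls as given. A reader of the final report could not rule the bias out afterwards. The results matter because section 8A1 intends the activity assessments to inform endpoints for a Phase III trial.

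**Working it through.** **1. What is fixed and what is open**

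| Item | Where | Status |
|---|---|---|
| Matching variables | 9A, 18B, 19B1, 19B2 | Age, sex, illness day, baseline coronary status or Z |
| Same, biomarkers | 18A | Age, sex, Z; illness day absent |
| Age caliper | 18A | ±2 years, biomarkers only |
| Z and illness-day calipers | – | Not stated |
| Ratio | 15A / 18A | 1:1 / 1:2 |
| Tie-break, order, lock date, selector | – | Not stated |
| Masking of selection to outcome | – | Not stated |

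**2. The plan's own figure.** Section 15A gives 80% power for 18 pairs (two-sided paired t-test, alpha 0.05). Reading the stated SD as that of the paired difference:
- IL-1RAP: d = 2.2/3.2 = 0.6875; noncentrality 0.6875 × √18 = 2.92; exact power 78.5%.
- IL-1R1: d = 5.6/8 = 0.70; noncentrality 0.70 × √18 = 2.97; exact power 79.9%.

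The figure reproduces within 2 points. This is a question of bias, not of sample size.

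**3. Illustration of the bias.** The assumptions, none of them in the documents, are: no drug effect; 18 cases; change scores normal with SD 1 per child and uncorrelated within sets; k acceptable candidates per case; and in a share f of sets the worst-outcome candidate (or the worst two, at 1:2) taken, otherwise a random one. The 18 is borrowed from the transcript calculation, because no number is given for echo.

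Expected shortfall of the controls taken in an affected set:
- 1:1, k = 2: 1/√π = 0.564 SD
- 1:1, k = 3: 3/(2√π) = 0.846 SD
- 1:2, k = 2: both are used, so 0
- 1:2, k = 3: (0.846 + 0)/2 = 0.423 SD

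The false contrast is f times this. At f = 0.5 and 1:1 it is 0.28 SD (k = 2) or 0.42 SD (k = 3). The SD of the paired difference is then 1.386 or 1.400, so the noncentrality is 0.282 × √18/1.386 = 0.86 or 0.423 × √18/1.400 = 1.28. The noncentral t with 17 df gives rejection of 12.9% and 22.8%. Simulation (40,000 trials per scenario) agrees:

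| Ratio | k | f = 0 | f = 0.25 | f = 0.5 |
|---|---|---|---|---|
| 1:1 | 2 | 5% | 7% | 13% |
| 1:1 | 3 | 5% | 9% | 23% |
| 1:2 | 2 | 5% | 5% | 5% |
| 1:2 | 3 | 5% | 6% | 11% |

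A within-set correlation of 0.3 leaves the 1:1 rates almost unchanged. The f = 0 column is what selection blind to outcome delivers.

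**4. Is k of 2 or 3 plausible?** Section 8A reports aneurysms in 9% and dilatation in 25% of the clinic's patients. Applied to 600 children, and treating the two groups as separate, that is 600 × 0.09 = 54 to 600 × 0.34 = 204 candidates. For 18 cases this is 54/18 = 3 to 204/18 ≈ 11 per case, before matching on age, sex and illness day, which would reduce it. This is a rough guide only.

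**The case against.** The strongest reply is that the documents nowhere say controls are picked with outcomes in view. That is right. A reader might infer that selection is unblinded, or that there is no matching rule, and neither inference is supported. The plan is silent on who selects and what that person sees. It does name the matching variables, and for biomarkers it sets an age caliper and a ratio. Section 11H also describes entry of study subjects' data into a database already holding over 1,200 children; that it holds 2- and 6-week Z scores for every candidate is likely but not stated.

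The reach is also limited. Transcript, ELISA and endothelial-cell results for the comparison are described as still to be measured (18A, 18B), so at selection only the recorded clinical course could act as a proxy for them. The sample sizes rest on those assays, and 15B says that the combination study is not powered for echo. Activity evidence also comes from pre/post measurements within patients and from the dose-activity model.

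The simulation gives the selector perfect knowledge of the tested outcome and always takes the worst candidate in the affected sets. That is harsher than inadvertent bias, and at 1:2 the effect shrinks or vanishes.

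All of this stands, and it narrows the point. What survives is that the plan contains no safeguard, and that its open calipers and conflicting ratios leave a choice to be made.

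**Conclusion.** The concern holds in limited form. For the secondary delta-Z comparison in both studies, control selection is neither fully specified nor masked to outcomes that are probably on file. The biomarker and endothelial-cell comparisons are exposed less directly, through clinical course. The primary safety outcome and the stated power are untouched.

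Under the assumptions above, rejection at a nominal 5% ranges from 5% to 23% when half the sets are affected, and from 5% to 9% when a quarter are. The size depends on the number of candidates, the affected share and the ratio, none of which the documents settle for echo. These figures show what could happen; they do not estimate what will.

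A reader might go further and conclude that the p-values are invalid or that the control list alone decides the activity result. The documents do not support either. The change should be made because it is cheap beforehand and the doubt cannot be removed afterwards.

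**What to change.** In sections 9A, 18A, 19B1 and 19B2:

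- Reconcile the ratio (with 15A, and with 15B and 18B for the combination study) and the list of matching variables, including whether illness day is one. State calipers for age, illness day and baseline Z.
- Have the study biostatistician run a seeded matching program with random tie-breaks. The extract should hold only eligibility, treatment-group, sample-availability and matching fields, with no follow-up echo, marker result or post-baseline course. Treatment group is needed to identify the control groups in 18B.
- Produce a pre-ranked reserve list for each case. Date and lock the matched sets and reserves before follow-up Z scores are merged or banked samples are pulled.
- Allow replacement only for a missing or unusable sample, in reserve order.

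The cost is plan wording, one restricted extract and a little programming. No patients or assays are added, and the sample size and stated power do not change.
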